1.2. Study Schema

SAD and MAD Schematic:

Motric Bio Study Scheme: Cohorts of 8 participants (6 MTR-601 and 2 placebo) will be sequentially enrolled following evaluation of safety and tolerability (S and T) by a Safety Review Committee (SRC). The SRC will determine whether any dose is safe and tolerable by evaluation of aggregate clinical, laboratory, ECG, echocardiography, spirometry, renal/urinary ultrasonography and PK (as available) data. The Single Ascending Dose (SAD) cohorts will begin dosing with 2 sentinel participants (1:1 - MTR-601: Placebo) followed 72 hours later by dosing the remainder of the cohort (5:1 - MTR-601: Placebo). Dosing will be performed after a standard breakfast, in all but one cohort, as preclinical studies indicated food enhanced exposure. The second SAD cohort will receive two doses of study drug – the first dose will be after overnight fasting and the second dose, following a washout period, after a standard breakfast. The Multiple Ascending Dose (MAD) cohorts will not begin until at least the SAD level 2 two-dose cohort has been completed and will not have sentinel dosing. MAD dosing will be daily for 14 days.

Abbreviations: AE = adverse event; CK-MB = creatinine kinase heart; CK-MM = creatinine kinase skeletal muscle; CRU = clinical research unit; D = Day; Hep = hepatitis; HIV = human immunodeficiency virus; LVEF = left ventricular ejection fraction; PCR = polymerase chain reaction; PK = pharmacokinetics; SARS-CoV-2 = severe acute respiratory syndrome coronavirus 2.

Note: When several assessments overlap, the suggested sequence of events will be as follows: ECG, vital sign collection, PK sample collection, laboratory blood sample collections, spirometry, dynamometry, urinalysis sample collection, and biopsy such that PK sample collection will be drawn as close to the nominal collection time point as possible.

- a. Height measured only at screening.
- b. To be performed as part of check-in procedures, prior to other Day -1 activities
- c. Urine drug screen for cotinine, alcohol, and drugs of abuse.
- d. Laboratory assessments will include serum chemistry, hematology, liver function tests, coagulation, and creatinine kinase (CK-MM and CK-MB). eGFR will use CKD-EPI calculation. For Cohort 4 only. Cystatin C will be measured on Day 1 at 4 and 12 hours post dose, and on Day 2.

- e. FSH testing for postmenopausal females only.
- f. Urinalysis by dipstick; if results are abnormal, follow up with microscopy. Samples are to be collected under colored lighting into opaque containers to blind participants to any discoloration of the urine.
- g. For women of childbearing potential: Serum pregnancy test at screening.
- h. Body composition assessments by bioimpedance and physical measurements.
- i. Performed during screening as a secondary visit or up to Day -1 check-in to confirm subject is still eligible.
- j. Telemetry and oximetry will continue into approximately 24 hour timepoint (Day 2), although it may be interrupted as needed to allow subjects to bathe.
- k. Plasma PK samples will be drawn at pre-dose (time 0); post-dose on Day 1 at 0.25, 0.50, 1, 1.5, 2, 4, 6, 8, and 12hours; 24 hours post-dose (Day 2); 48 hours post-dose (Day 3); 72 hours post-dose (Day 4); and 96 hour post-dose (Day 5).
- l. Urine will be collected for PK analysis on Day 1 from a pre-dose void and post-dose from 0–4 hours, 4–8 hours, 8–12 hours, and 12–24 hours; from 24–48 hours post-dose; from 48–72 hours post-dose ; and from 72–96 hours post-dose . Samples are to be collected at intervals under amber-colored lighting into opaque containers to blind participants to any discoloration of the urine.
- m. Mandatory muscle biopsy on Day 2 only.
- n. IPSS questionnaire will be performed at the specified timepoints per SOA- results greater than 8 will necessitate an unscheduled urinary system ultrasound as soon as is feasible.
- o. Urinary system Ultrasound will be performed at specified timepoints in SOA unless the IPSS result (greater than 8) necessitates additional unscheduled ultrasonography.
- p. Screening eligibility will be determined by off-site (LabCorp) lab Total CK and CK-MB values and normal ranges while check-in eligibility will be determined by Day-1 on-site (WCT) lab Total CK and CK-MB values and normal ranges. Furthermore, CK isoenzymes (e.g., MM, MB) will not be evaluated as part of dose escalation decisions – rather total CK will be used.

	Screening	CI	CRU Inpatient															
Day	(-30 to -2)	D (-1)	D1												D2	D3	D4	D5
Hour			0	0.25	0.50	1	1.5	2	3	4	6	8	12	← Washout →				
Plasma PK ^k																		
Urine PK ^l			X							X		X	X	X	X	X	X	
Genetic biomarker (buccal swab)		X																
Plasma Biomarker			X			X								X				
Spirometry		X								X			X	X	X		X	
Electronic nerve stimulation response		X								X				X			X	
Dynamometry		X								X		X	X	X	X	X	X	
IPSS ^m		X												X	X	X	X	
Urinary system Ultrasound ⁿ		X													X			
MTR-601 administration			X															
Adverse events																		
Concomitant medications	X	X																

Abbreviations: AE = adverse event; CI = Check-in; CK-MB = creatinine kinase heart; CK-MM = creatinine kinase skeletal muscle; C-SSRS = Columbia Suicide Severity Rating Scale; D = Day; LVEF = left ventricular ejection fraction; PK = pharmacokinetics.

Note: When several assessments overlap, the suggested sequence of events will be as follows: ECG, vital sign collection, PK sample collection, laboratory blood sample collections, spirometry, dynamometry, urinalysis sample collection, and biopsy, such that PK sample collection will be drawn as close to the nominal collection time point as possible.

- Height measured only at screening.
- To be performed as part of check-in procedures, prior to other Day -1 activities
- Urine drug screen for cotinine, alcohol and drugs of abuse.
- Laboratory assessments will include serum chemistry, hematology, liver function tests, coagulation, and creatinine kinase (CK-MM and CK-MB). eGFR will use CKD-EPI calculation.
- FSH testing for postmenopausal females only.
- Urinalysis by dipstick; if results are abnormal, follow up with microscopy. Samples are to be collected under colored lighting into opaque containers to blind participants to any discoloration of the urine.
- For women of childbearing potential: Serum pregnancy test.
- Body composition assessments by bioimpedance and physical measurements (after negative SARS-CoV-2 test results).
- Performed during screening as a secondary visit or up to Day -1 to confirm subject is still eligible.

- j. Telemetry and oximetry will continue into approximately 24 hour timepoint (Day 2) although it may be interrupted as needed to allow subjects to bathe.
- k. Plasma PK samples will be drawn at pre-dose (time 0); post-dose on Day 1 at 0.25, 0.50, 1, 1.5, 2, 4, 6, 8, and 12hours; 24 hours post-dose (Day 2); 48 hours post-dose (Day 3); and 72 hours post-dose (Day 4).
- l. Urine will be collected for PK analysis on Day 1 from a pre-dose void and post-dose from 0–4 hours, 4–8 hours, 8–12 hours, and 12–24 hours; from 24–48 hours post-dose ; from 48–72 hours post-dose ; and from 72–96 hours post-dose. Samples are to be collected at intervals under colored lighting into opaque containers to blind participants to any discoloration of the urine.
- m. IPSS questionnaire will be performed at the specified timepoints per SOA- results greater than 8 will necessitate an unscheduled urinary system ultrasound as soon as is feasible.
- n. Urinary system Ultrasound will be performed at specified timepoints in SOA unless the IPSS result (greater than 8) necessitates additional unscheduled ultrasonography.
- o. Check-in eligibility will be determined by Day-1 on-site Total CK and CK-MB, not by Day -1 outside laboratory Total CK and isoenzymes.

Table 2 continued... Schedule of Assessments SAD Level 2, Two-Dose Cohort – Days 6–10 and Follow-up

	CRU Inpatient																FU	
Day	D6											D7	D8	D9	D10		D12	
Hour	0	0.25	0.50	1	1.5	2	3	4	6	8	12	0	0	0	0	4		
Full physical examination																X		
Neurological exam																X		
Height/weight																X		
Laboratory assessments ^a								X			X	X	X	X	X	X		
Urinalysis ^b	X					X		X		X	X	X	X	X	X	X		
12-lead electrocardiogram																X		
C-SSRS																	X	
LVEF/Echocardiogram												X						
Cardiac telemetry ^c																		
Oximetry ^c																		
Vital Signs	X			X	X			X	X	X	X	X	X	X	X	X		
Plasma PK ^d																		
Urine PK ^e	X							X		X	X	X	X	X	X	X		
Spirometry								X			X		X			X		
Electronic nerve stimulation response								X				X				X		
Muscle biopsy ^f												X						
Dynamometry								X		X	X	X	X	X	X	X		
Plasma Biomarker	X			X								X				X		
IPSS ^g									X			X	X	X	X	X		
Urinary system Ultrasound ^h													X			X		
MTR-601 administration	X																	
Adverse events																		
Concomitant medications																		

	CRU Inpatient																FU
Day	D6											D7	D8	D9	D10		D12
Hour	0	0.25	0.50	1	1.5	2	3	4	6	8	12	0	0	0	0	4	
CRU check-out/discharge																X	
Follow-up telephone call																	X

Abbreviations: AE = adverse event; CI = Check-in; CK-MB = creatinine kinase heart; CK-MM = creatinine kinase skeletal muscle; C-SSRS = Columbia Suicide Severity Rating Scale; D = Day; LVEF = left ventricular ejection fraction; PK = pharmacokinetics.

Note: When several assessments overlap, the suggested sequence of events will be as follows: ECG, vital sign collection, PK sample collection, laboratory blood sample collections, spirometry, dynamometry, urinalysis sample collection, and biopsy, such that PK sample collection will be drawn as close to the nominal collection time point as possible.

- Laboratory assessments will include serum chemistry, hematology, liver function tests, coagulation, and creatinine kinase (CK-MM and CK-MB). eGFR will use CKD-EPI calculation
- Urinalysis by dipstick; if results are abnormal, follow up with microscopy. Samples are to be collected at intervals under colored lighting into opaque containers to blind participants to any discoloration of the urine.
- Telemetry and oximetry will continue for approximately 24 hours post-dose (Day 7) although it may be interrupted as needed to allow subjects to bathe.
- Plasma PK samples will be drawn at pre-dose (time 0); post-dose on Day 1 at 0.25, 0.50, 1, 1.5, 2, 4, 6, 8 and 12 hours; 24 hours post-dose (Day 7); 48 hours post-dose (Day 8); 72 hours post-dose (Day 9); and 96 hours post-dose (Day 10).
- Urine will be collected for PK analysis on Day 6 from a pre-dose void and post-dose from 0–4 hours, 4–8 hours, 8–12 hours, and 12–24 hours; from 24–48 hours post-dose; from 48–72 hours post-dose; and from 72–96 hours post-dose. Samples are to be collected at intervals under colored lighting into opaque containers to blind participants to any discoloration of the urine.
- Mandatory muscle biopsy on Day 7 (time 0) only.
- IPSS questionnaire will be performed at the specified timepoints per SOA- results greater than 8 will necessitate an unscheduled urinary system ultrasound as soon as is feasible.
- Urinary system Ultrasound will be performed at specified timepoints in SOA unless the IPSS result (greater than 8) necessitates additional unscheduled ultrasonography.

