5.2.12 Pharmacokinetic Parameters

The following plasma PK parameters will be calculated for MRT-601 after single ascending doses (SAD):

Parameter	Definition
C_{max}	Maximum observed plasma concentration
T_{max}	Time of the maximum plasma concentration
AUC_{0-24}	Area under the plasma concentration-time curve from time-zero to 24 h postdose
AUC_{last}	Area under the plasma concentration-time curve from time-zero to the time of the last quantifiable concentration; calculated using the linear trapezoidal rule
AUC_{inf}	Area under the plasma concentration-time curve from time-zero extrapolated to infinity; calculated as: $AUC_{inf} = AUC_{last} + C_{last}/\lambda_z$ Note: Additional criteria for reporting AUC_{inf} are summarized in Section 5.14
$AUC_{Extrap} (\%)$	Percentage of AUC_{inf} based on extrapolation; calculated as: $AUC_{Extrap} = 100 \times [1 - (AUC_{last}/AUC_{inf})]$
λ_z (Lambda-z, k_{el})	Apparent elimination rate constant; calculated as the negative slope of the linear regression through the terminal log-linear segment of the plasma concentration-time curve Note: Additional criteria for reporting λ_z are summarized in Section 5.14

QMD Ref: Worldwide-TMP-ST-054-1.0_Effective: 12Aug2022	Governing QMD: Worldwide-SOP-ST-026
Confidentiality Statement This document is the property of Worldwide Clinical Trials Inc. and may not be duplicated, copied, altered or removed from company without prior approval from Worldwide Quality Assurance or in compliance with Worldwide Standard Operating Procedures.	

Worldwide Clinical Trials Controlled Quality Management Document			
		Sponsor:	MTR-601-NHV-101
		Protocol Number:	Motric Bio
STATISTICAL ANALYSIS PLAN			

Parameter	Definition
$T_{1/2}$	Observed terminal elimination half-life; calculated as: $T_{1/2} = \ln(2)/\lambda_z$
CL/F	Apparent total body clearance after extravascular administration, calculated as: $CL/F = \text{Dose}/AUC_{inf}$, where F is the bioavailability
V_z/F	Apparent volume of distribution after extravascular administration, calculated as: $V_z/F = \text{Dose}/(AUC_{inf} \times \lambda_z)$, where F is the bioavailability
C_{last}	Last observed quantifiable plasma concentration
T_{last}	Time of the last observed quantifiable plasma concentration

The following plasma PK parameters will be calculated for MRT-601 after multiple ascending doses (MAD) for Day 1 and Day 7:

Parameter	Definition
C_{max}	Maximum observed plasma concentration
T_{max}	Time of the maximum plasma concentration

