5.14 Pharmacokinetic Analyses

5.14.1 Concentration-Time Data

5.14.1.1 Plasma

MRT-601 plasma concentration-time data will be tabulated by nominal time and treatment (dose level) for SAD and by nominal time, treatment (dose level), and study day for MAD using descriptive statistics. For presentation of the individual data and summary statistics, concentrations below the limit of quantitation (BLQ) will be set to zero. Nominal and relative time will be presented in hours.

MRT-601 samples will be collected at:

SAD: 0 (pre-dose) and at 0.25, 0.50, 1, 1.5, 2, 4, 6, 8, 12, 24, 48, 72, and 96 hours post-dose.

SAD (2 dose, food effect): 0 (pre-dose 1) and at 0.25, 0.50, 1, 1.5, 2, 4, 6, 8, 12, 24, 48, 72, and 96 hours postdose

MAD, Day 1: 0 (predose) and at 0.25, 0.50, 1, 1.5, 2, 4, 6, 8, and 12 hours postdose for Cohorts 1 and 2. A 24 hour sample (Day 2, predose) was added for Cohort 3 onward.

QMD Ref: Worldwide-TMP-ST-054-1.0_Effective: 12Aug2022	Governing QMD: Worldwide-SOP-ST-026
Confidentiality Statement This document is the property of Worldwide Clinical Trials Inc. and may not be duplicated, copied, altered or removed from company without prior approval from Worldwide Quality Assurance or in compliance with Worldwide Standard Operating Procedures.	

Worldwide Clinical Trials Controlled Quality Management Document			
		Sponsor:	MTR-601-NHV-101
		Protocol Number:	Motric Bio
STATISTICAL ANALYSIS PLAN			

MAD Day 7: 0 (predose) and at 0.25, 0.50, 1, 1.5, 2, 4, 6, 8, and 12 hours postdose for Cohorts 1 and 2. A 24 hour sample (Day 8, predose) was added for Cohort 3 onward.

MAD Day 14: 0 (pre-dose) and at 0.25, 0.50, 1, 1.5, 2, 4, 6, 8, 12, 24, 48, 72, and 96 hours post-dose.

Mean plasma concentration-time data will be presented graphically on linear and semi-logarithmic scales using nominal times. Individual subject concentration-time data will be presented graphically on linear and semi-logarithmic scales using actual times. For individual subject concentration-time data, spaghetti plots (all subjects in one plot per treatment) and all treatments in one plot for each subject will be created.

For SAD, mean profiles and spaghetti plots will be created.

For SAD (food effect): mean profiles, spaghetti plots, and individual plots (fed vs. fasted) will be created.

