5.14.2 Pharmacokinetic Methodology

QMD Ref: Worldwide-TMP-ST-054-1.0_Effective: 12Aug2022	Governing QMD: Worldwide-SOP-ST-026
Confidentiality Statement This document is the property of Worldwide Clinical Trials Inc. and may not be duplicated, copied, altered or removed from company without prior approval from Worldwide Quality Assurance or in compliance with Worldwide Standard Operating Procedures.	

Worldwide Clinical Trials Controlled Quality Management Document			
		Sponsor:	MTR-601-NHV-101
		Protocol Number:	Motric Bio
STATISTICAL ANALYSIS PLAN			

Concentration-time data for MRT-601 in plasma will be analyzed using noncompartmental methods in Phoenix™ WinNonlin® (Version 8.3.4 or higher, Certara, L.P.)² in conjunction with Certara Integral™ (Version 23.10.1, Certara, USA, Inc.)³. The PK Population will be used in the PK analysis.

During the PK analysis, concentrations below the limit of quantification (BLQ) up to the time of the first quantifiable concentration will be treated as zero. Embedded (values between 2 quantifiable concentrations) and terminal BLQ concentrations will be treated as “missing”. Calculation of the PK characteristics will be based on actual elapsed times [h] relative to dosing.

Lambda-z (λ_z) and AUC_{inf} Reporting Criteria

The following criteria will be used to report λ_z :

- At least three quantifiable concentrations will be used in the regression
- C_{max} or data prior to C_{max} will not be included in the regression.
- The adjusted regression coefficient (R² adj) should be ≥ 0.80 .

If these acceptance criteria are not met, λ_z reported for individual subjects will be retained in PK parameter tables for informational purposes; λ_z will be excluded from summary statistics. Parameters calculated using λ_z (T_{1/2}, CL/F, V_z/F) will be reported as ND (not determinable). Lambda-z (λ_z) and descriptive parameters (λ_z time range, Adj R², etc.) will be presented in a separate listing.

If lambda-z acceptance criteria are met and AUC_{inf} is estimable, the following criteria are used to report AUC_{inf}:

- The percentage of AUC_{inf} based on extrapolation should be <30.0%.

If the percentage of AUC_{inf} based on extrapolation is 30.0% or greater, AUC_{inf} and AUC_{Extrap} will be retained in a PK parameter table for informational purposes; these parameters will be excluded from summary statistics, subsequent PK calculations (e.g., CL/F, and V_z/F), and statistical analysis (e.g., ANOVA).

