5.14.3.2 Food Effect (SAD, 2 Dose)

As all treatments for SAD and MAD study parts are administered under fed conditions, a comparison of fasted and fed C_{\max} , AUC_{last} , and AUC_{inf} will be performed.

Analyses of variance (ANOVA) will be performed on the natural log transformed AUC_{last} , AUC_{inf} , and C_{\max} using MIXED procedure in SAS. The MIXED model will contain treatment as a fixed effect. The geometric mean ratios (Test (Fasted-Period 1)/Reference (Fed-Period 2)) and their 90% confidence intervals will be provided.

The Wilcoxon signed rank test will be used for a nonparametric comparison of T_{\max} values; a significant difference is defined a priori as $p < 0.05$.

Conclusions regarding the results of the statistical analysis (ANOVA) of PK parameters across treatments will be based on the ratio of the geometric means (Test / Reference) and the 90% confidence interval about the ratio. No significant difference will be demonstrated if the 90% confidence intervals are fully contained within the limits of 80.00% to 125.00%.

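### Protocol and SAP disagree on whether fasted plasma sampling ends at 72 h or 96 h; if it ended at 72 h, the fasted/fed AUClast ratio can be biased downward (about 0 to 7%)

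*Protocol*

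**What the plan says.** **Fasted dose (Day 1).** Protocol Table 2 footnote k gives a complete list of plasma times that closes with "48 hours post-dose (Day 3); and 72 hours post-dose (Day 4").

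**Fed dose (Day 6).** The plasma PK footnote in the continuation of Table 2 closes with "72 hours post-dose (Day 9); and 96 hours post-dose (Day 10").

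**SAP sampling list.** SAP 5.14.1.1 has one list for this cohort: "SAD (2 dose, food effect): 0 (pre-dose 1) and at 0.25, 0.50, 1, 1.5, 2, 4, 6, 8, 12, 24, 48, 72, and 96" hours. It is anchored to the first dose, and there is no separate list for the second. SAP section 8 records no changes, so the difference from footnote k is not explained there.

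**Analysis.** SAP 5.14.3.2 plans "a comparison of fasted and fed" Cmax, AUClast and AUCinf. Each is a geometric mean ratio of fasted (Period 1) over fed (Period 2), with a 90% confidence interval judged against 80.00% to 125.00%. No common time window is set.

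**AUClast.** SAP 5.2.12 defines it as "Area under the plasma concentration-time curve from time-zero to the time of the last quantifiable concentration", by the linear trapezoidal rule. Under SAP 5.14.2, "terminal BLQ concentrations will be treated as" missing, so a sample below quantification (BLQ) at the end of a profile adds no area.

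**The concern.** AUClast depends on when sampling stops as well as on exposure. If the protocol footnotes describe what was done, the numerator of the ratio cannot extend past 72 h and the denominator can reach 96 h. For identical profiles, that inequality can only lower the ratio or leave it unchanged.

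The direction matters because the protocol (sections 1.2 and 2.4) already expects food to raise exposure. A ratio pulled below 1 by the schedule would look like confirmation, and nothing in the planned output would separate the two. The same ratio and its interval are what SAP 5.14.3.2 uses to decide whether fasted and fed exposure differ.

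**Working it through.** The documents give no food-effect sample size or bias figure, so there is none to reproduce.

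**Inputs from the documents**
- Last plasma sample: 72 h fasted and 96 h fed (Table 2 footnotes). The day labels are consistent: Day 1 + 72 h = Day 4, and Day 6 + 96 h = Day 10.
- Accumulation below 2-fold with once-daily dosing (Protocol 2.3).
- Steady-state exposure at 20 mg of about 1/15 of the NOAEL (Protocol 2.3). Half the NOAEL exposure is Cmax 421 ng/mL and AUC0-24 6,600 ng·h/mL (Protocol 4.2).
- Six active subjects in the cohort (Protocol 4.1).

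**Assumptions.** Half-life, absorption rate, assay limit (LLOQ) and within-subject CV are not given. I take one-compartment decay, half-lives of 8 to 24 h, ka = 1/h and LLOQ of 0.1 to 2 ng/mL.

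**Bound on half-life.** Accumulation R = 1/(1 − 2^(−24/t½)). R = 2 gives t½ = 24 h, so R < 2 means t½ below 24 h in this model.

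**Window effect.** For identical profiles (true ratio 1) quantifiable to the last sample:

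ratio = (1 − 2^(−72/t½)) / (1 − 2^(−96/t½))

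At 24 h this is (1 − 0.125)/(1 − 0.0625) = 0.875/0.9375 = 0.933. The trapezoidal column applies the SAP's rule at the protocol's nominal times. The predicted concentration at 96 h uses a 20 mg AUC of 2 × 6,600/15 = 880 ng·h/mL.

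| t½ (h) | R | Ratio, exact | Ratio, trapezoidal | Predicted C at 96 h (ng/mL) |
|---|---|---|---|---|
| 8 | 1.14 | 0.998 | 0.998 | 0.02 |
| 12 | 1.33 | 0.988 | 0.986 | 0.21 |
| 18 | 1.66 | 0.961 | 0.958 | 0.87 |
| 24 | 2.00 | 0.933 | 0.930 | 1.64 |

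**BLQ rule applied.** Where the 96 h value is BLQ, the ratio returns to 1.000. At LLOQ 0.1 ng/mL the 12, 18 and 24 h rows keep their bias. At 0.5 ng/mL the 18 and 24 h rows do, at 1 ng/mL only the 24 h row, and at 2 ng/mL none.

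**Against the decision limits.** At the 24 h bound, ln(0.933) = −0.069 and ln(0.80) = −0.223, so the shift uses 31% of the distance to the lower limit. In simulated paired log-differences with n = 6 and true ratio 1, the chance that the 90% interval lies within 80–125% falls from 0.90 to 0.74 at a within-subject CV of 10%, and from 0.19 to 0.17 at a CV of 20%.

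**AUCinf.** Extrapolation restores the missing tail when the lambda-z criteria are met. At a 24 h half-life the extrapolated share from 72 h is 2^(−3) = 12.5%, against the SAP's 30% limit. Reaching 30% would need t½ = 72 × ln 2 / ln(1/0.3), about 41 h.

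**Matched window.** With 0–72 h (or 0–96 h) in both periods the artefact is exactly zero. Carry-over is separate and remains: the second dose comes 120 h after the first, and with matched 0–96 h windows it alone gives ratios of 0.999, 0.990 and 0.969 at 12, 18 and 24 h.

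**The case against.** The strongest reply is that there may be no unequal window. The SAP lists 96 h for this cohort. The footnote for the other SAD cohorts also runs to 96 h, subjects are in-house on Day 5, and urine after the fasted dose is collected through 96 h ("and from 72–96 hours post-dose. Samples are to be collected at intervals under colored lighting"). The fed-dose footnote itself labels the post-dose times of a Day 6 dose as Day 1, so these footnotes contain copying slips. The Plasma PK row of Table 2 has no readable marks in the public text to settle it. All of this stands as evidence that a 96 h fasted sample is possible. It does not show that one was drawn, and footnote k reads as a finished list.

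Second, profiles ending at different times are normal for AUClast, and the schedule adds nothing if the fed 96 h sample is BLQ. That also stands. The avoidable part is the unequal schedule.

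Third, little rests on the result. The study is non-powered, food effect is not a listed secondary endpoint, and every other cohort is dosed fed. With six subjects the interval is wide unless within-subject variability is low. This limits the consequence but does not justify an avoidable one-directional artefact.

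A reader might also infer that stopping at 72 h makes fasted profiles fail the 30% extrapolation rule. The extrapolated share at the 24 h bound (12.5%) does not support that.

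**Conclusion.** The conflict between footnote k and SAP 5.14.1.1 is certain, and so is the absence of a common window. The bias is conditional: it needs footnote k to have been followed and the fed 96 h sample to be quantifiable. Given both, it runs downward, by about 1% at a 12 h half-life, 4% at 18 h and at most about 7% at 24 h. The last figure is a limit, because the protocol reports accumulation below 2-fold.

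The sizes rest on one-compartment decay and identical profiles. A slower terminal phase in a multi-compartment drug could exceed 7%; a stress case of 36 h gives 0.890, although its one-compartment accumulation of 2.7 lies outside the reported range. Cmax is unaffected and AUCinf is largely protected.

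Two stronger readings are tempting: that the AUClast ratio is definitely biased, and that the SAP list is the one in error. The documents support neither, since they do not show which schedule was followed and give no LLOQ.

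**What to change.** 1. Establish from the sampling records whether a fasted 96 h plasma sample was drawn, and reconcile footnote k and SAP 5.14.1.1 accordingly. Neither text should be changed before that is known.
2. If it was not drawn, add AUC0-72 for both periods to SAP 5.14.3.2, truncating the fed profile at 72 h. State a rule, the same in both periods, for profiles that are BLQ before 72 h; SAP 5.14.2 would otherwise leave those values missing. Base the partial-AUC food-effect conclusion on AUC0-72, report AUClast descriptively, and keep Cmax and AUCinf as planned.
3. If it was drawn, use AUC0-96 in both periods, with the equivalent BLQ rule.

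The unblinded interim review in Protocol 2.3 covered SAD cohorts 1–4, so the amendment should say that the window is dictated by the sampling schedule. Continuing to report AUClast keeps the change visible. SAP section 5 allows amendment before database lock.

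The cost is SAP wording and one extra partial AUC from samples already taken. The downside of AUC0-72 is that the 72–96 h fed tail goes unused in that comparison. Matching the windows does not remove carry-over; the Day 6 pre-dose sample, 120 h after the first dose, can be used to check it.
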